# **Study Timeline**

The entire study is estimated to be completed in five years. The first six months of the project were dedicated to hiring staff, therapist training, and certification. Recruitment began in the 7th month of Year 1. Approximately 3-4 new participants will be recruited per month. Recruitment began in August 2017. We anticipate recruiting a total of 5 participants in Year 1, 15 participants in Years 2 through 4, and 10 participants in the beginning of Year 5. The majority of Year 5 will be devoted to follow-up assessments, the completion of data entry and data management procedures, preliminary analyses, and the preparation of manuscripts.

# Table 1. Visit Projection Table

#### **Subjects**

A total of 60 participants will be enrolled, with a target male to female ratio of 33:27. This ratio reflects the higher prevalence rates of AUDs in biological men compared to biological women. Forty participants will be randomized to the UP condition and 20 to the Take Control condition. In addition, 25 participants from the UP group will receive two fMRI scans (pre- and post-treatment).

Participants will be recruited via flyers, brochures, lab website and StAR Facebook page, MBTA advertisements, etc. Telephone screenings will determine initial eligibility, and potential research participants will be invited to CARD, located at Boston University, for a more extensive assessment of alcohol use and emotional disorders.

## Setting

All study procedures, except for MRI procedures, will be conducted at CARD, which is one of the largest research clinics devoted to anxiety and related emotional disorders in the world and maintains a substantial research participant flow. CARD consists of approximately 15,000 sq. ft. of space and includes multiple individual and group treatment rooms and full-time administrative staff including two receptionists covering the front desk during the 12-hour clinic day (8 a.m. through 8 p.m.). Staff members include licensed psychologists, a psychiatrist, a nurse, research technicians, doctoral students from clinical psychology and counseling psychology, and psychiatric residents. The MRI procedures will be conducted at Boston University's Center for Integrated Life Sciences & Engineering (CILSE).

#### **Inclusion/ Exclusion Criteria**

# **Inclusion Criteria:**

- 1) DSM-5 diagnosis of an alcohol use disorder (AUD)
- 2) DSM-5 diagnosis of Social Anxiety Disorder (SAD), Panic Disorder/Agoraphobia (PD/A), Generalized Anxiety Disorder (GAD), and/or Obsessive Compulsive Disorder (OCD) as determined by a clinician-administered diagnostic assessment using the Anxiety Disorder Interview Schedule for DSM-5 (ADIS-5). Clinically significant diagnoses will be determined by assignment of an ADIS clinical severity rating (CSR) of 4 (definitely disturbing/disabling on the 0-8 CSR scale) or higher on at least the principal diagnosis
- 3) Adults 21 years or older
- 4) Expressed desire to stop drinking alcohol completely or to reduce alcohol consumption
- 5) Reported drinking an average of at least 15 standard drinks per week for males, or 8 for females occurring over a 28-consecutive day period during the 90 day-long time window that preceded the screening session
- 6) Must be willing to discontinue any form of psychotherapy, except AA, for either anxiety or depression prior to screening

# **Exclusion Criteria**:

(Exclusion criteria are the specific criteria, which would disqualify an individual from participating in the study, not simply the opposite of the inclusion criteria):

- 1) DSM-5 diagnosis of current major depressive disorder (with the exception of substanceinduced depressive disorder) that requires immediate treatment with pharmacologic agents, bipolar disorder, schizophrenia, current bulimia/anorexia, dementia, or other substance dependence, with the exception of nicotine, marijuana, and caffeine dependence
- 2) Presence of suicidal ideation or history of suicide attempts (i.e. two or more hospitalizations related to significant suicidal ideation or following suicide attempts within the last five years or one such hospitalization within the last six months)
- 3) Non-English speakers
- 4) Previously received an adequate trial of cognitive-behavioral therapy (CBT; 8 sessions within the past 5 years)
- 5) Contraindications to MRI scans
- 6) History of head injury with >5-minute loss of consciousness
- 7) Pregnancy. Note: Women of childbearing potential (not postmenopausal for at least one year) will be required to provide a negative urine pregnancy test prior to each scan
- 8) Implantation of anything containing magnetically sensitive material including metal plates, aneurysm clips, cardiac pacemakers, and stents; history of sheet metal work; claustrophobia
- 9) Cognitive impairment (MoCA<21)
- 10) Serious medical illness or instability for which hospitalization may be likely within the next year

# **Exclusion from Participating in Active Treatment:**

- 1) Reduction in the mean number of drinks consumed per week by 50% or more between the phone screen and the in-person screening
- Report of average drinks per day falling within safe levels of alcohol consumption (i.e., 2 drinks/day for males and 1 drink/day for females by the HHS standard) two weeks prior to screening

# Recruitment

The majority of participants are expected to be self-referred and treatment seeking. Referrals may be recruited through a variety of methods such as: word-of-mouth referrals from former participants, referral from area medical and mental health professionals, advertisements in local newspapers, radio advertisements, MBTA advertisements, brochures/flyers, web advertisements (Facebook page, study website, craigslist ad, BU Quickie Jobs page), digital billboard advertisements, movie theatre advertisements, and through the CARD intake process.

The StAR2 recruitment team consists of This team is responsible for recruiting participants for this study, through the following methods:

1) Web Ads: Online advertisements:

- Facebook page: https://www.facebook.com/bostonstarstudy/
- Study website: https://studyforalcoholreduction.com/
- NIH website: https://www.nih.gov/
- 2) Radio Ads: Advertisements will be submitted to local radio stations.
- 3) Newspaper Ads: Advertisements will be put in local area newspapers.
- 4) Brochures/Flyers: Flyers will be posted on local bus stops, telephone poles and passed around the community.
- 5) MBTA Ads: Advertisements will be placed on MBTA trains, buses, and stations.
- 6) Digital Billboard Ads: Digital advertisements (e.g., the study flyer) will be used for recruitment.
- 7) Movie Theater Ads: Advertisements will be played on screens in movie theaters.
- 8) CARD referrals: CARD intakes that meet criteria for AUD and an anxiety disorder and have been assigned to the StAR waitlist.

# **CARD Referrals**

Participants referred through the CARD intake process that have both an alcohol use disorder and a DSM-5 diagnosis of Social Anxiety Disorder (SAD), Panic Disorder/Agoraphobia (PD/A), Generalized Anxiety Disorder (GAD), and/or Obsessive Compulsive Disorder (OCD) as determined by a clinician-administered diagnostic assessment using the Anxiety Disorder Interview Schedule for DSM-5 (ADIS-5), will be placed on the StAR waitlist. CARD Clinical Director, [name], will email the Research Assistants (RAs) to let them know a case has been added to the waitlist. The RAs should check the waitlist on a weekly basis.

The RAs will call the eligible cases on the waitlist to conduct a 15-20 minute phone screen. The RA can call the participant candidate 3 times within a 2-week window to attempt to make contact. If the participant meets the phone screen criteria, the RAs will schedule the participant candidate for an in-person screening session.

All contacts for research participants must be logged into the Titanium waitlist Referral Comment box along with dates. The final disposition should be clear in the notes. If a participant drops, or the RA is not able to contact the participant after calling 3 times in 2 weeks, it is the study's responsibility to send a letter confirming our closure of their case. A template can be found here:

Upon completion, all waitlists

should be sent back to [name] by putting her name in the Assigned Clinician spot. The RA should also email [name] to let her know.

# **Initial Evaluation Period**

Potential participants will be given information about the nature of the study over the telephone and will undergo an initial phone screening (see phone screening procedures for more information) to determine initial eligibility. Eligible participants will then be invited to the

Center for Anxiety and Related Disorders at Boston University for an in-clinic screening to further assess their eligibility for the study. At the screening, participants will be provided an informed consent form which will be verbally reviewed before signing. Participants who are eligible following the screening session will be randomized to one of two study conditions (UP or TC). A description of measures and procedures associated with the screening session can be found in the Assessment Measures Administration section of this manual and in the Participant Binder.

As of March 18th, 2020, screening procedures were changed from in-person to remotely, through Zoom. Individual breathalyzers are sent via mail to the participant prior to the consenting appointment, as well as a Qualtrics link via email containing the digital version of the consent form. Using a Qualtrics survey, participants are able to digitally sign consent which researchers are then able to sign the same form and email the completed form to the participant.

#### **Treatment Conditions and Specifications**

Participants will be assigned to one of two groups: UP or TC. Participants in the UP group may also be asked to undergo two brain MRI scans of less than two hours of duration. The first MRI scan will occur after the participant has been randomized but before the first treatment session, and the second brain MRI scan will occur within a two week window after the last treatment session.

#### **Phone Screening**

In order to conduct a phone screen with someone that has been referred to StAR2, the RA will attempt to contact the participant up to 3 times within a two week period. Should more contact attempts be necessary, the PD should be consulted. In the event that a participant is never successfully contacted, the RA will document this as "Unable to contact" in the StAR2 Recruitment Tracking Contact Log, and highlight their initials in red. Once the RA reaches a participant, he/she will attempt to complete the phone screen (15-20 minutes), which includes reading the IRB approved phone screen script, and filling out the phone screen is saved on the Shared Drive file path:

The phone screens should be saved with

Upon completion of the phone screen, the RA determines whether the participant is eligible based on established inclusion/exclusion criteria and interest to participate. Potential participants who pass the telephone screening will be identified by their initials until they are enrolled after the in-person screening session and assigned an ID number. If they are scheduled for an in-person screening session this should be recorded in the StAR2 Recruitment Tracking Google sheet, on the Recruitment Tracking Tab.

If a phone screen has already been conducted and the RA is unable to make contact for scheduling the intake appointment (after 3 call attempts in 2 weeks), the RA should document the no contact in the log.

All cases that are not eligible for an in-person screening session will be provided a referral for the type of treatment they are seeking, if requested. The list of referral options is saved in:

#### Informed Consent/Screening Session

The day before the in-person screening appointment, the RA will call the participant to confirm the appointment and remind him/her about the approximate length of the appointment. The screening session is expected to take approximately 4 hours to complete (Informed consent = 15 mins; Health assessment = 45 min; Self-report questionnaires = 1 hour; IE assessment = 1-2 hours).

On the day of the screening appointment, the RA greets the participant. Next, the participant's blood alcohol concentration (BAC) will be measured using a breathalyzer to ensure that the participant provides written informed consent while sober (BAC=0.00%). If the BAC is 0.00%, the RA will administer the Informed Consent Form. Discussion during the informed consent will include information about the treatment options, randomization procedures, and a brief rationale for these approaches. Participants will be invited to ask questions about the study procedures and expectations. Participants will also be provided information on the nature of the investigation, the types of assessments and treatments involved, and the potential risks involved in participating; they will then be asked to sign an informed consent statement prior to

A photocopy

of the consent form will be given to the participant to keep. Participants will be informed that participation in the study is voluntary and that they have the right to withdraw from the study at any time without penalty.

After the consent form is signed and all the participant's questions about the study have been answered, the RA will accompany the participant to the medication room where the study nurse will complete the health screen. The health screen involves a medical history questionnaire, a blood and urine sample, vitals and weight, and the Montreal Cognitive Assessment (MoCA). If the nurse is unable to complete the MoCA at this time, the RA can conduct this assessment (if they have been trained to do so). The nurse will also have the participant complete a Release of Information Form for their primary care physician.

Next, the RA will take the participant to a UP treatment room. The RA will then conduct the Alcohol Timeline Follow-Back assessment with the participant. The RA will need to collect drinking data for the past 90 days. Then, the RA will download the RealLife Exp application on the participants' phone to activate the EMA component of the study. The survey should be activated on the screening session. Seven days after the screening session the RA should email the participant to deactivate the survey (see EMA procedures for more information). We cannot deactivate the survey pack remotely, which is why the participant needs to be instructed on when and how to do so. Deactivating the survey pack will only stop notifications from being sent to the participant during non-EMA weeks, it will not delete the account.

The RA will give the participant the EMA instructions handout and the "What is AUD" handout to take home, both of which can be found in the Screening tab of the participant binder. The RA then loads the Screening Self-report Qualtrics survey on the study computer in room 233D for the participant. All surveys are set up to ensure that participants answer every question, eliminating the possibility of blank responses. However, the RA must ensure the participant has reached the last page of the survey before moving on to the next portion of the session. Upon completion of the questionnaires, the participant notifies the RA and may take a break. The RA notifies the IE that the participant is ready for the assessment and emails the link to the IE assessment survey, which includes the ADIS, SIGH-A, and SIGH-D. Alternatively, the IE can access all assessment surveys through Qualtrics. When the IE finishes the assessment, he/she will alert the RA that the assessment is complete. The RA will thank the participant for his/her time, and inform the participant that he/she will receive a phone call about eligibility in the next 1-2 weeks after the team has established consensus for study enrollment.

Note: As of March 18th, 2020, screening procedures were changed from in-person to remotely, through Zoom. Individual breathalyzers are sent via mail to the participant prior to the consenting appointment, as well as a Qualtrics link via email containing the digital version of the consent form. Using a Qualtrics survey, participants are able to digitally sign consent which researchers are then able to sign the same form and email the completed form to the participant.

#### **Consensus Meeting**

Each week, the research and medical team will meet for approximately one hour to discuss all new participants that were evaluated for the study to come to consensus on study enrollment. The RA should bring the screening participant(s) binder(s) to the meeting, as well as the CSR sheet. The IE that conducted the ADIS will fill out the participant's diagnoses and CSRs pre and post consensus meeting on the CSR sheet. The CSR sheet can be found in the screening tab of the Participant Binder. This meeting will allow the IEs and medical staff an opportunity to discuss eligibility concerns and review inclusion/exclusion criteria. Once the team has come to consensus, the RA will contact the participant. If the pre and post consensus meeting CSRs do not match, the RA will be responsible for going into the Qualtrics Data and changing the CSRs to match what was decided in the meeting. The old Qualtrics ADIS data for the screening participant should be archived so as not to be confused with the correct, updated version.

#### Eligibility

If the participant is not eligible, the RA will contact the participant, and will provide the participant with an appropriate referral if relevant, which can be found in:

If the participant is not satisfied with

the explanation for why they are not eligible, the RA will inform them the PD will contact them to explain further.

If the participant is eligible, they will be randomized into either the UP or TC condition. They will be contacted for scheduling schedule for either session 1 or the baseline MRI (only a subset of UP participants will be contacted about the MRI).

## **Treatment/Intervention**

Following the initial screening session (see description of assessment procedures for more information regarding the screening session), participants are randomized to one of two treatment conditions: 1) Unified Protocol, or 2) Take Control.

## **Unified Protocol (UP)**

The UP is a 16 session, transdiagnostic, cognitive-behavioral therapy that has shown efficacy in treating emotional disorders. The efficacy of the UP to facilitate abstinence from alcohol consumption in individuals with comorbid AUD/AXD has also been examined, with results from this study indicating a reduction from baseline in drinks consumed per day (Ciraulo et al, 2013).

## Take Control (TC)

TC is a 12 session, psychotherapy platform derived from the National Institute on Alcohol Abuse and Alcoholism's (NIAAA) self-help approach, *Rethinking Drinking*. In this study, TC, originally designed as a computerized treatment, has been modified by our team to be administered by a therapist to control for effects that may be related to patient-therapist interaction (as opposed to elements of the treatment itself). Specifically, on a weekly basis, therapists will review material from TC and offer general advice on implementation of the alcohol reduction skills in daily life.

#### Randomization

Prior to the start of the trial, a random number generator was used to establish a randomization schedule that assigns participants to either the active treatment (UP) or comparison condition (TC). Once a new participant is enrolled in the trial, the RA will refer to the next assignment in the randomization schedule

The current trial aims to recruit 40 participants in the UP condition and 20 participants in the TC condition.

Once the participant is randomized, the RA will contact the participant to discuss scheduling and provide further information about length of the trial. TC participants will complete 12 sessions of therapy (in a maximum of 16 weeks), while UP participants will complete 16 weeks of therapy (in a maximum of 21 weeks). Additionally, follow-up assessments will be completed at one month and six months posttreatment.

If the participant is randomized to TC, the next session is session 1, and the RA will schedule the session based on the participant's and assigned therapist's availability. If the participant is randomized to the UP condition, the RA will potentially schedule the participant

for the fMRI session prior to scheduling session 1 with the therapist. The first study session will be scheduled within 4-weeks after the in-clinic baseline assessment. If the one-month window expires before the participant can complete the first session, then the assessment must be repeated to assess the participant's continued eligibility for the study (a "refresher").

To schedule an fMRI session, the RAs will need to refer to the CILSE scheduling calendar to confirm that the scanner and the MRI technicians are available and to book the appointment. The RA will need to book 30 minutes in the

Med Lab at CARD for the urine, drug, and/or pregnancy test, and 1.5 hours at CILSE for the scan. Once appointments are scheduled, the RA will document the time and date for all involved study staff in Titanium (see How to Log a Treatment Session in Titanium).

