# **Study Overview**

## **Data Analysis Aims:**

1. Demonstrate that Unified Protocol (UP) treatment reduces alcohol consumption relative to Take Control (TC), as measured by our primary outcome measure, mean number of drinks consumed per week.

Comparisons will be made for data obtained for the treatment period for the two conditions. Specifically, the hypothesis that participants in the UP condition will evidence greater reductions in our primary efficacy measure (mean weekly number of standard drinks) than participants receiving TC will be examined using conditional latent growth models (LGM), modeled using MPlus 7.0 (Muthén & Muthén, 1998-2012). Research personnel will examine changes in the weekly mean number of drinks consumed per day over the course of treatment (i.e., study sessions 1 to 16). They will also examine whether the proportion of subjects achieving safe levels of drinking (males = 2 drinks per day; females = 1 drink per day) is significantly greater in the UP condition than in the TC group (guidelines from USDA, 2010). This will be done by calculating odds ratio effect sizes (with 95% confidence interval) contrasting safe levels of drinking in the UP vs. TC groups.

2. Demonstrate that the UP, relative to TC, reduces alcohol intake on other measures of alcohol consumption and evaluate the extent to which this also leads to a comparative decrease in measures of craving.

Conditional LGM will be used to test the hypothesis that UP will both demonstrate greater reductions in the secondary efficacy measures of percent days heavy drinking per week (defined as more than 3 drinks per drinking day for biological women and more than 4 drinks per drinking day for biological men [NIAAA guidelines]), percent days of drinking per week, and in alcohol craving (as assessed by the Alcohol Urge Questionnaire and the Obsessive Compulsive drinking scale) than the TC condition.

3. Demonstrate that the UP results in greater reductions in anxiety and depression as measured by the SIGH-A, SIGH-D, ODSIS, and OASIS than TC, and that there will be a correlation between these reductions and the decreases seen in mean weekly number of standard drinks consumed per day, percent days heavy drinking per week, percent days drinking per week, and alcohol craving.

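### The Aim 1 growth curve starts at session 1, a post-randomization visit that a UP-only scan may delay, and the pre-randomization 90-day drinking record is not named in the model

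*Combined protocol and SAP*

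**What the plan says.** **The model.** Study Overview, Data Analysis Aims, Aim 1 states: "Comparisons will be made for data obtained for the treatment period for the two conditions". It then examines weekly drinking "over the course of treatment (i.e., study sessions 1 to 16") with a conditional latent growth model. The hypothesis is a greater reduction in UP. Aim 1 names no pre-randomization drinking value, either as a growth point or as a covariate.

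**The path to session 1.** It differs by arm. Under Randomization: "If the participant is randomized to TC, the next session is session 1". In the same section, the research assistant may book a UP participant "for the fMRI session prior to scheduling session 1 with the therapist". Treatment Conditions and Specifications agrees: "The first MRI scan will occur after the participant has been randomized but before the first treatment session". Subjects plans 40 UP and 20 TC participants, with 25 of the UP group scanned before and after treatment.

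**What both arms share.** Session 1 is to fall within 4 weeks of the baseline assessment, and the assessment is repeated if that window lapses (Randomization). Staff are told to book session 1 as early as they can (Scheduling/Tracking Sessions). The eligibility call comes 1 to 2 weeks after screening (Informed Consent/Screening Session).

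**Drinking data held before randomization.** At screening: "The RA will need to collect drinking data for the past 90 days". The Timeline Follow-Back (TLFB) is then repeated at every treatment session (Description of Instruments, I).

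**The concern.** The primary contrast is a difference in reduction, so the first point of the curve is part of the definition of the effect. Here that point is a visit after randomization, and one arm has an extra step on the way to it. A scan has to fit scanner, technician and Med Lab availability, so it could push session 1 back.

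Change between screening and session 1 is plausible. Participants want to stop or cut down and qualify on a heavy 28-day period within the previous 90 days. At screening they complete a 90-day drinking recall, receive a handout on alcohol use disorder and start a week of app-based monitoring. If drinking drops early and then levels off in everyone, an arm that waits longer enters its curve lower and on a flatter stretch. Its measured reduction is then smaller for reasons unrelated to treatment, and a real UP benefit could be understated in a trial with only 20 controls.

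This concerns the start of the curve. It is separate from the different number of sessions in the two arms.

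**Working it through.** The documents give no delay, no expected pre-treatment change, and no SD or effect size for this outcome. There is no stated figure to reproduce; only 40 + 20 = 60 and 25/40 = 0.625 can be checked. The steps below ask when the start point matters and how large the effect could be.

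**Inputs from the documents:** scanned share of UP 0.625; 4-week limit from screening to session 1 in both arms; 1 to 2 weeks used before the eligibility call, which leaves roughly 2 to 3 weeks.

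**Assumptions, not from the documents:** no true arm difference; TC and unscanned UP participants start at week 2; scanned UP participants start *e* weeks later.

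**Step 1. Which shapes of decline give a bias.** Least-squares slope over 12 weekly points, starting 2 or 4 weeks after screening, from 30 drinks/week. UP average = 0.375 × (2-week slope) + 0.625 × (4-week slope).

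| Common decline in both arms | Slope, 2-week wait | Slope, 4-week wait | UP average |
|---|---|---|---|
| Linear, 1 drink/week per week | -1.00 | -1.00 | -1.00 |
| 7% per week, raw scale | -1.29 | -1.11 | -1.18 |
| 7% per week, log scale | -0.073 | -0.073 | -0.073 |
| Early and steep, 12 + 18·exp(-0.3t) | -0.77 | -0.42 | -0.55 |

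A linear decline gives no bias, nor does a proportional decline modelled on the log scale. If the total fall before session 1 is the same in both arms, both curves start equally low and again there is none. The bias needs a longer UP wait and a decline that slows.

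**Step 2. Size if the decline slows.** Let y = 10·exp(-t/τ), so drinking falls by 10 drinks/week in all. The fall from session 1 to session 12 for a start at week s is 10·[exp(-s/τ) - exp(-(s+11)/τ)]. TC uses s = 2. UP = 0.375 × (fall at s = 2) + 0.625 × (fall at s = 2 + e).

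| τ (weeks) | TC | UP, e = 0.5 | UP, e = 1 | UP, e = 2 |
|---|---|---|---|---|
| 3 | 5.00 | 4.52 | 4.12 | 3.48 |
| 4 | 5.68 | 5.26 | 4.89 | 4.28 |
| 6 | 6.02 | 5.72 | 5.44 | 4.95 |

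The UP reduction looks smaller by about 5-10%, 10-18% and 18-30% for e = 0.5, 1 and 2 weeks (0.3-0.5, 0.6-0.9 and 1.1-1.5 drinks/week). At e = 0 it is zero.

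**Step 3. Dependence on the session 1 look-back.** Step 2 takes session 1 as a point value. The look-back of the session 1 TLFB is not stated. If it averages back to screening, and later values are weekly averages, the same curves give about 2-4%, 4-8% and 7-15%.

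**Step 4. A second set of assumptions.** Screening level 30, a fall of r per week before session 1, both arms ending at 12. TC at session 1 = 30(1-r)²; UP = 0.375·30(1-r)² + 0.625·30(1-r)^(2+e).

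| e | r | TC at session 1 | UP at session 1 | Gap | Gap / TC reduction |
|---|---|---|---|---|---|
| any | 0 | 30.00 | 30.00 | 0 | 0% |
| 1 | 5% | 27.07 | 26.23 | 0.85 | 5.6% |
| 1 | 10% | 24.30 | 22.78 | 1.52 | 12.3% |
| 2 | 5% | 27.07 | 25.43 | 1.65 | 10.9% |
| 2 | 10% | 24.30 | 21.41 | 2.89 | 23.5% |

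Measured from screening, both arms fall by 30 - 12 = 18 and the gap is 0 in every row. If both arms instead fall by the same 50% after session 1, the gap from session 1 is half as large.

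**Scanned share.** The fMRI section says about half of eligible UP participants are asked. At a share of 0.5, the gaps in Steps 2 to 4 are multiplied by 0.5/0.625 = 0.8.

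**The case against.** A reader might infer that the scan does delay session 1 in UP, and that any equal pre-treatment fall will then show as a smaller UP reduction. The documents support neither statement. No section gives a later UP start. A scan is only a possibility for a UP participant, it takes about two hours, and it could fit inside a wait for a therapist that either arm may face. The 4-week limit and the instruction to book early apply to both arms. Scanning covers only part of UP and was suspended from 2020 until 2021 (Study Procedures). An equal total fall gives no bias at all.

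Nor do the documents show that drinking falls between screening and session 1. The exclusion rule "Reduction in the mean number of drinks consumed per week by 50% or more between the phone screen and the in-person screening" covers an earlier interval, before randomization. The repeat assessment after a lapsed window checks eligibility.

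Two further points stand. The session 1 TLFB is retrospective and may already reach back into the gap, which would roughly halve the illustrated figures. Premature Study Termination also refers to a data analysis section of the grant, which is not among the documents and may specify how baseline is handled.

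These objections remove any claim of a demonstrated bias. They do not remove the design point: as written, the curve starts at a post-randomization visit with an arm-specific step before it, although a pre-randomization measure exists for everyone.

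**Conclusion.** The point holds as a gap in the Aim 1 specification. The model starts after randomization, at a visit that may come later in UP, and does not name the 90-day screening record. The size of any delay is unknown and may be zero.

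If UP does start later and drinking falls and flattens after screening in both arms, the UP reduction from session 1 is understated. The illustrations run from 0 to about 30% of the TC reduction, or 0 to about 3 drinks/week. The upper ends need a 2-week extra wait and a steep early fall, and the lower end is equally compatible with the documents. With no extra wait, an equal total fall before session 1, or a linear decline, there is no bias.

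The direction is against UP. This mechanism would not produce a false claim of superiority, but it could hide part of a real benefit. The change is worth making because it removes the dependence on session 1 timing at low cost, and a baseline covariate should also improve precision.

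**What to change.** In Aim 1:

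1. Enter the screening TLFB, for example mean weekly drinks over its last 28 days, as the common pre-randomization baseline. Use it either as a covariate or as a first time point with one mean for both arms.
2. Run time in weeks from randomization, and include the days between screening and session 1 where the session 1 TLFB covers them.
3. Report the UP-TC difference in drinks per week at a fixed week after randomization.
4. Report the screening-to-session-1 interval by arm, so that any delay is visible.
5. Keep the session 1 start as a sensitivity analysis.

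**Cost.** Mostly analysis-plan wording, since the screening and per-session TLFB are already collected. The model becomes slightly more complex because it gains a pre-treatment segment. If the session 1 TLFB does not already reach back to the screening date, extending it is a small change in data collection. At a fixed week, a participant who started late will have had fewer sessions; the session-based sensitivity analysis shows how much this matters.
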